10.1.6 End of Treatment Visit

Patients who complete the study or discontinue study treatment should be scheduled for an EOT visit as soon as possible, at which time all of the assessments listed for the EOT visit will be performed. At the time of study early withdrawal, the reason for early withdrawal and any new or continuing AEs should be documented. If study drug administration is discontinued, the reason for discontinuation will be recorded.

10.1.7 Safety Follow-up Visit

All patients who discontinue study treatment will have a safety follow-up visit for safety evaluations 30 days (+/- 14 days) after the last dose of study drug or surgery, whichever comes last. If study drug administration is discontinued, the reason for discontinuation will be recorded.

10.2 Details of Procedures

10.2.1 Study Materials

BMS will provide nivolumab and ipilimumab.

10.2.2 Safety Assessments

Adverse events will be assessed at each patient visit, documented in the medical record, and entered into CRFs. Patients who report visual changes on therapy will be referred to Ophthalmology for evaluation of potential inflammatory or immune-related adverse events (uveitis, optic neuritis, etc.) In addition, any occurrence of a SAE from the time of the first protocol specific intervention forward, until 100 days after the last dose of study drug, will be reported. Refer to safety reporting Section 10.3.

Safety will be evaluated for all treated patients using the NCI CTCAE version 4.0 (<http://ctep.cancer.gov>). Safety assessments will be based on medical review of AE reports and the results of vital sign measurements, physical examinations and clinical laboratory tests.

10.3 Criteria for Evaluation

10.3.1 Safety Evaluation

Refer to Common Terminology Criteria Adverse Events (CTCAE) version 4.0 (<http://ctep.cancer.gov>)

10.3.1.1 Medical History, Physical Exam, Physical Measurements

Physical examination will be performed at the time points outlined in Section 10.0. If the screening physical is conducted within 24 hours of dosing on Cycle 1 Day 1, then a single examination may count as both the screening and pre-dose evaluation. Pertinent medical history (physician discretion) will be recorded.

10.3.1.2 Vital Signs

Blood pressure, heart rate, respiratory rate, oxygen saturation by pulse oximetry and temperature will be obtained as outlined in Section 10.0. Orthostatic (supine and standing) blood pressure and heart rate are to be measured for any subject who experience lightheadedness, dizziness, syncope or any similar complaints.

10.3.1.3 ECOG Status

ECOG performance status will be evaluated continuously and documented at Screening and at each visit as outlined in Section 10.0.

10.3.1.4 Assessment of Baseline Symptoms

Baseline signs and symptoms present within 2 weeks of starting therapy, whether or not related to current disease will be documented. Assessment of these baseline signs and symptoms will be done at each treatment and Follow-Up Visit (see Section 10.1). Any worsening by > 1 Grade change from baseline is to be documented as an adverse event.

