10.3.1.5 Adverse Event Monitoring

An adverse event is the appearance or worsening of any undesirable sign, symptom, or medical condition occurring after starting the study drug even if the event is not considered to be related to study drug. Medical conditions/diseases present before starting study drug are only considered adverse events if they worsen after starting study drug. Abnormal laboratory values or test results constitute adverse events only if they induce clinical signs or symptoms, are considered clinically significant, or require therapy.

Adverse events will be evaluated according to the NCI CTCAE Version 4.0 on a continuous basis starting from when the patient takes the first dose of nivolumab or ipilimumab to follow up visits. Events, such as abnormal laboratory values, considered by the principal investigator to be not clinically significant (related to the study or study drug) will not be documented. **The investigator (or physician designee) is responsible for verifying and**

providing source documentation for all adverse events and assigning the attribution for all adverse events for subjects enrolled. If abnormal lab values, which were not pre-existing or which worsened after the first dose of study drug, meet Common Terminology Criteria (CTC) for reporting as adverse events (AE), they will be documented in the AE source document and captured in the CORE/PDMS Database. For the lab results that do not meet the CTC for reporting as an AE, they will be considered not clinically significant (NCS). No additional documentation will be required to neither specify NCS lab results nor require physician investigator signature.

Adverse events will be treated appropriately. Such treatment may involve changes in nivolumab or ipilimumab therapy including possible interruption or discontinuation, starting or stopping concomitant treatments, changes in the frequency or nature of assessments, hospitalization, or any other medically required intervention. Refer to Sections 6.1-3 for treatments of nivolumab or ipilimumab infusion reaction and toxicities.

Once an adverse event is detected, it should be followed until its resolution, and assessment should be made at each visit of any changes in severity, the suspected relationship to nivolumab or ipilimumab, the interventions required to treat it, and the outcome. Reporting of adverse events will be done according to NCI CTCAE version 4.0. The following items will be recorded at least:

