- Event description
- Date of onset of AE
- CTCAE grade/severity (1, 2, 3, 4, 5)
- Relationship to treatment with nivolumab or ipilimumab (unrelated, unlikely, possible, probable, highly probable/definite)
- Action taken (none, temporarily discontinued agent, drug treatment given/specify, permanently discontinued agent, non-drug treatment given/specify, hospitalization)
- Date of AE stop
- Outcome (recovered without sequelae, recovered with sequelae, ongoing, worsened, death)
- Serious AE (yes, no)
- Serious Adverse Events (SAEs) must be collected from the time of the first protocol specific intervention until 100 days after the last dose of study drug.

Potential Drug Induced Liver Injury (DILI)

Wherever possible, timely confirmation of initial liver-related laboratory abnormalities should occur prior to the reporting of a potential DILI event. All occurrences of potential DILIs, meeting the defined criteria, must be reported as SAEs.

Potential drug induced liver injury is defined as:

- 1) AT (ALT or AST) elevation > 3 times upper limit of normal (ULN)

AND

- 2) Total bilirubin > 2 times ULN, without initial findings of cholestasis (elevated serum alkaline phosphatase),

AND

- 3) No other immediately apparent possible causes of AT elevation and hyperbilirubinemia, including, but not limited to, viral hepatitis, pre-existing chronic or acute liver disease, or the administration of other drug(s) known to be hepatotoxic.

Recommended Adverse Event Recording Guidelines

Attribution	Grade 1	Grade 2	Grade 3	Grade 4	Grade 5
Unrelated	Phase I	Phase I	Phase I	Phase I	Phase I
			Phase II	Phase II	Phase II
				Phase III	Phase III
Unlikely	Phase I	Phase I	Phase I	Phase I	Phase I
			Phase II	Phase II	Phase II
				Phase III	Phase III
Possible	Phase I	Phase I	Phase I	Phase I	Phase I
	Phase II	Phase II	Phase II	Phase II	Phase II
		Phase III	Phase III	Phase III	Phase III
Probable	Phase I	Phase I	Phase I	Phase I	Phase I
	Phase II	Phase II	Phase II	Phase II	Phase II
		Phase III	Phase III	Phase III	Phase III
Definitive	Phase I	Phase I	Phase I	Phase I	Phase I
	Phase II	Phase II	Phase II	Phase II	Phase II
		Phase III	Phase III	Phase III	Phase III

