11.3 Investigator Communication with Supporting Companies

- Adverse events classified as "serious" require expeditious handling and reporting to BMS to comply with regulatory requirements.
- All SAEs whether related or unrelated to nivolumab or ipilimumab must be immediately reported to BMS (by the investigator or designee) within 24 hours of becoming aware of the event, using the M. D. Anderson SAE forms. If only limited information is initially available, follow-up reports are required. The original SAE form must be kept on file at the study site.

All SAEs should be faxed (or emailed) to BMS at:

Global Pharmacovigilance & Epidemiology

Bristol-Myers Squibb Company

[contact]

Email: [contact]

- For studies conducted under an Investigator IND, any event that is both serious and unexpected must be reported to the FDA as soon as possible and, in no event, later than 7 days (death or life-threatening event) or 15 days (all other SAEs) after the investigator's or institution's initial receipt of the information. The investigator will provide BMS with a simultaneous copy of all adverse events filed with the FDA. SAEs will be reported on the MDACC SAE Form.

- AE Reporting Period: For nivolumab and ipilimumab, all AEs must be collected which occur after the first dose through within 100 days of discontinuation of dosing or completion of the patient's participation in the study if the last scheduled visit occurs at a later time. In addition, the Investigator should notify BMS of any SAE that may occur after this time period which they believe to be certainly, probably, or possibly related to nivolumab and/or ipilimumab.
 - [contact]

Notes:

- Cancer/Overdose: An overdose is defined as the accidental or intentional ingestion of any dose of a product that is considered both excessive and medically important. For reporting purposes, any form of overdose, regardless of adverse outcome, will be considered as an important medical event and reported immediately to BMS.
- Hospitalizations (exceptions): Criteria for hospitalizations not reported as SAEs include admissions for:
 - Planned as per protocol medical/surgical procedure
 - Routine health assessment requiring admission for baseline/trending of health status documentation (e.g., routine colonoscopy)
 - Medical/surgical admission for purpose other than remedying ill health state (planned prior to entry into study trial; appropriate documentation required)

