12.2 Endpoints

12.2.1 Primary Endpoint: Safety

Safety will be recorded through the incidence of adverse events, serious adverse events and specific laboratory abnormalities (worst grade) in each treatment arm. Toxicities will be graded using the NCI CTCAE version 4.0. For trial monitoring and decisions about future trials, extreme toxicities (TOX) will be defined as any grade 3 or higher adverse event that is possibly, probably, or definitely related to any therapy received on this protocol and occur within the first 6 weeks of therapy with one exception. Any grade 3 or higher adverse event that is potentially treatable with steroids will only count as an extreme toxicity if it does not improve to grade 1 or better within 2 weeks. Additionally, a delay of greater than 3 months from the expected surgery date will count as a TOX.

Success will be predefined as having at least 13 of 15 subjects receiving their assigned therapy without grade 3 or higher adverse events necessitating a delay in the pre-established surgical resection date (a clinically driven end-point defined by the multidisciplinary MD Anderson hepatocellular cancer team).

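### Minor internal contradictions: Section 10.3.1.4 sets a higher bar than 10.3.1.5 and 11.3 for recording a worsened baseline symptom, and Section 8.0 ends study participation where 8.1, 5.3, 10.1.7 and Table 1 continue it

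*Combined protocol and SAP*

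**What the plan says.** **Recording threshold.** Section 10.3.1.4 covers signs and symptoms already present at baseline: "Any worsening by > 1 Grade change from baseline is to be documented as an adverse event". Section 10.3.1.5 has no grade threshold. Its general definition is "An adverse event is the appearance or worsening of any undesirable sign, symptom, or medical condition occurring after starting the study drug", and on pre-existing disease it says "Medical conditions/diseases present before starting study drug are only considered adverse events if they worsen after starting study drug". Section 11.3 adds that "all AEs must be collected which occur after the first dose through within 100 days of discontinuation of dosing", or to the end of the patient's "participation in the study if the last scheduled visit occurs at a later time". The primary endpoint in 12.2.1 defines TOX as "any grade 3 or higher adverse event that is possibly, probably, or definitely related to any therapy received on this protocol" arising in the first 6 weeks. A steroid-treatable event counts only if it fails to improve to grade 1 or better within 2 weeks. A surgery delay of more than 3 months is a TOX in its own right.

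**Stopping drug or leaving the study.** Section 8.0 lists reasons for which a patient must come off treatment and also out of the study. One is an adverse event, laboratory abnormality or illness that, in the investigator's view, makes further treatment unsuitable for the patient. Section 8.1 has almost the same investigator-judgment trigger under a heading that stops only the drugs. Section 7.0 provides that certain patients with a grade 3 or higher drug-related event miss the next dose and go on to surgery once the event allows. Sections 5.3 and 10.1.7 give a safety visit to everyone who discontinues treatment. Table 1 then has follow-up visits every 9 weeks with adverse-event review, and survival contact every 12 weeks.

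**The concern.** The primary objective is safety, and 12.1 reports that enrollment stopped because the safety endpoint had been reached. The rules that decide what enters the safety record, and how long a patient is observed, should therefore agree.

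On the first conflict, 10.3.1.4 is the only section written specifically for baseline symptoms, so site staff could reasonably apply it by itself. A worsening that 12.2.1 would count could then have no adverse-event record.

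On the second, two sections give different consequences for nearly the same clinical judgment. If withdrawal under 8.0 is taken to end follow-up, two things are at stake: later progression and survival information, and the part of TOX that can be judged only well after the planned surgery date.

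**Working it through.** The plan gives no figure to reproduce here. The check is a list of grade changes and a comparison of sections.

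**1. Which worsenings fall below the 10.3.1.4 threshold**

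Grade change = end grade − baseline grade. Baseline grades 1 to 4 allow 10 possible worsenings.

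| Worsening | Change | More than one grade? | Ends at grade 3 or higher? |
|---|---|---|---|
| 1→2 | 1 | no | no |
| 2→3 | 1 | no | yes |
| 3→4 | 1 | no | yes |
| 4→5 | 1 | no | yes (death) |
| 1→3, 2→4, 3→5 | 2 | yes | yes |
| 1→4, 2→5 | 3 | yes | yes |
| 1→5 | 4 | yes | yes |

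Six of the 10 meet the threshold and four do not. Of those four, 1→2 is below the TOX level, and 4→5 is a death, which is captured as a serious adverse event under 11.1. That leaves 2→3 and 3→4, so for TOX the conflict matters only for a symptom already at grade 2 or higher at baseline. Under 10.3.1.5 and 11.3 both are adverse events and must be collected.

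**2. What withdrawal under 8.0 could cost**

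| Item | If 8.0 ends follow-up | If the other sections govern |
|---|---|---|
| The triggering event | Documented: 10.1.6 records new and continuing events at early withdrawal; 10.3.1.5 says "Once an adverse event is detected, it should be followed until its resolution"; 11.1 cuts serious-event capture short only for withdrawn consent | Documented |
| TTP (12.2.2.2) | Censored at the last tumor assessment before withdrawal | Continues as far as restaging continues |
| PFS (12.2.2.3) | Censored at the last follow-up before withdrawal | Continues |
| Surgery delay of more than 3 months (12.2.1) | May never be judged | Can be judged, if surgery status is recorded |

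The last row matters only when the event is not already a TOX. A related grade 3 or higher event in the first 6 weeks that is not excused by the steroid exception counts whatever happens to surgery. The delay criterion adds information only for unrelated, lower-grade or steroid-resolved events.

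**3. Restaging after discontinuation**

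Section 5.3 calls for restaging every 12 weeks and does not say whether this stops with treatment. Table 1 marks tumor imaging at the discontinuation visit and at no later column, for either arm. Section 10.1.2 repeats the 12-week interval but refers back to Section 10, so it does not settle the matter. Correcting 8.0 alone would leave it unclear how TTP and PFS are assessed after drug is stopped.

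**The case against.** Most of the case on the other side stands, and it limits the point.

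- Section 10.3.1.4 does not say that smaller worsenings are to be left out. It can be read as a sufficient condition, with 10.3.1.5 governing. The table headed "Recommended Adverse Event Recording Guidelines" lists possibly, probably and definitively related grade 3 to 5 events under every phase. Laboratory values have their own rule in 10.3.1.5. A site that follows all these sections records the 2→3 worsening, so the gap opens only if 10.3.1.4 is applied by itself. The present wording may be a slip for ≥ 1.
- Section 7.0 keeps certain patients with grade 3 or higher drug-related events on the path to surgery, and 10.1.6, 10.3.1.5 and 11.1 keep the event itself documented.
- The success rule of at least 13 of 15 patients concerns events that force a delay to the planned resection date. It contains no 3-month wait, so the unjudged delay does not enter it directly.

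Two stronger readings are tempting. A reader might set the 100-day window against the day on which a 3-month delay becomes known and conclude that the delay falls outside observation. The documents do not support this: that window governs adverse-event collection, and nothing makes it the limit for finding out a surgery date. A reader might also infer that the declared safety result is biased toward success. The documents give neither the number of patients with baseline symptoms at grade 2 or higher nor the number withdrawn under 8.0, so neither size nor direction can be stated.

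What remains is that the sections contradict one another, and that 8.0 is an operational rule expressed as mandatory.

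**Conclusion.** Minor, but wrong as written. Both contradictions are in the text. The first is close to editorial: its consequence is confined to one-grade worsenings to grade 3 or 4, and only where 10.3.1.4 is read in isolation. The second has somewhat more substance. Followed literally, 8.0 would end TTP and PFS follow-up for a toxicity-related reason and could leave the surgery-delay part of TOX unjudged for a patient whose event is not itself a TOX. This rests on reading withdrawal from the study as the end of all follow-up, which 8.0 does not define and the other sections speak against. No size or direction of bias is claimed for the endpoint or for the 13-of-15 rule.

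**What to change.** 1. In 10.3.1.4 replace > 1 grade with ≥ 1 grade, so that it agrees with 10.3.1.5 and 11.3.
2. Reconcile 8.0 with 7.0, 8.1, 5.3, 10.1.7 and Table 1, so that stopping study drug for an adverse event does not end the follow-up those sections already schedule. Leave the other withdrawal reasons in 8.0 and all treatment-stopping criteria as they are.
3. Record surgery status or date at the existing follow-up visits until the 3-month criterion can be judged.
4. Reconcile restaging after discontinuation between 5.3 and Table 1, and correct the cross-reference in 10.1.2.

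**Cost:** wording changes and one data field. Because enrollment has closed, new wording alone does little for treatment windows already past. It needs a limited source review of the 27 randomized patients: symptoms at grade 2 or higher at baseline, and surgery dates and last assessments for anyone withdrawn for an adverse event. If the reconciliation adds imaging after discontinuation that Table 1 does not now mark, that is a further small cost.

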10.3.1.5 Adverse Event Monitoring

An adverse event is the appearance or worsening of any undesirable sign, symptom, or medical condition occurring after starting the study drug even if the event is not considered to be related to study drug. Medical conditions/diseases present before starting study drug are only considered adverse events if they worsen after starting study drug. Abnormal laboratory values or test results constitute adverse events only if they induce clinical signs or symptoms, are considered clinically significant, or require therapy.

Adverse events will be evaluated according to the NCI CTCAE Version 4.0 on a continuous basis starting from when the patient takes the first dose of nivolumab or ipilimumab to follow up visits. Events, such as abnormal laboratory values, considered by the principal investigator to be not clinically significant (related to the study or study drug) will not be documented. **The investigator (or physician designee) is responsible for verifying and**

providing source documentation for all adverse events and assigning the attribution for all adverse events for subjects enrolled. If abnormal lab values, which were not pre-existing or which worsened after the first dose of study drug, meet Common Terminology Criteria (CTC) for reporting as adverse events (AE), they will be documented in the AE source document and captured in the CORE/PDMS Database. For the lab results that do not meet the CTC for reporting as an AE, they will be considered not clinically significant (NCS). No additional documentation will be required to neither specify NCS lab results nor require physician investigator signature.

Adverse events will be treated appropriately. Such treatment may involve changes in nivolumab or ipilimumab therapy including possible interruption or discontinuation, starting or stopping concomitant treatments, changes in the frequency or nature of assessments, hospitalization, or any other medically required intervention. Refer to Sections 6.1-3 for treatments of nivolumab or ipilimumab infusion reaction and toxicities.

Once an adverse event is detected, it should be followed until its resolution, and assessment should be made at each visit of any changes in severity, the suspected relationship to nivolumab or ipilimumab, the interventions required to treat it, and the outcome. Reporting of adverse events will be done according to NCI CTCAE version 4.0. The following items will be recorded at least:

- Event description
- Date of onset of AE
- CTCAE grade/severity (1, 2, 3, 4, 5)
- Relationship to treatment with nivolumab or ipilimumab (unrelated, unlikely, possible, probable, highly probable/definite)
- Action taken (none, temporarily discontinued agent, drug treatment given/specify, permanently discontinued agent, non-drug treatment given/specify, hospitalization)
- Date of AE stop
- Outcome (recovered without sequelae, recovered with sequelae, ongoing, worsened, death)
- Serious AE (yes, no)
- Serious Adverse Events (SAEs) must be collected from the time of the first protocol specific intervention until 100 days after the last dose of study drug.

Potential Drug Induced Liver Injury (DILI)

Wherever possible, timely confirmation of initial liver-related laboratory abnormalities should occur prior to the reporting of a potential DILI event. All occurrences of potential DILIs, meeting the defined criteria, must be reported as SAEs.

Potential drug induced liver injury is defined as:

- 1) AT (ALT or AST) elevation > 3 times upper limit of normal (ULN)

AND

- 2) Total bilirubin > 2 times ULN, without initial findings of cholestasis (elevated serum alkaline phosphatase),

AND

- 3) No other immediately apparent possible causes of AT elevation and hyperbilirubinemia, including, but not limited to, viral hepatitis, pre-existing chronic or acute liver disease, or the administration of other drug(s) known to be hepatotoxic.

Recommended Adverse Event Recording Guidelines

Attribution	Grade 1	Grade 2	Grade 3	Grade 4	Grade 5
Unrelated	Phase I	Phase I	Phase I	Phase I	Phase I
			Phase II	Phase II	Phase II
				Phase III	Phase III
Unlikely	Phase I	Phase I	Phase I	Phase I	Phase I
			Phase II	Phase II	Phase II
				Phase III	Phase III
Possible	Phase I	Phase I	Phase I	Phase I	Phase I
	Phase II	Phase II	Phase II	Phase II	Phase II
		Phase III	Phase III	Phase III	Phase III
Probable	Phase I	Phase I	Phase I	Phase I	Phase I
	Phase II	Phase II	Phase II	Phase II	Phase II
		Phase III	Phase III	Phase III	Phase III
Definitive	Phase I	Phase I	Phase I	Phase I	Phase I
	Phase II	Phase II	Phase II	Phase II	Phase II
		Phase III	Phase III	Phase III	Phase III

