10.3.2 Laboratory Test Assessments

Any abnormal laboratory test result considered clinically significant by the Investigator must be recorded.

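### Section 10.3.1.5 gives two conflicting rules for laboratory adverse events, so AE incidence and TOX depend on which is applied, and one rests on open-label investigator judgement

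*Combined protocol and SAP*

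**What the plan says.** Section 10.3.1.5 (Adverse Event Monitoring) contains four statements about laboratory values, in this order:

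- The definition: "Abnormal laboratory values or test results constitute adverse events only if they induce clinical signs or symptoms, are considered clinically significant, or require therapy".
- The exclusion, which names laboratory findings as its example: an event "considered by the principal investigator to be not clinically significant (related to the study or study drug) will not be documented".
- The grading sentence. Its scope is set by the opening condition, "If abnormal lab values, which were not pre-existing or which worsened after the first dose of study drug". Values within that scope that "meet Common Terminology Criteria (CTC) for reporting as adverse events (AE), they will be documented in the AE source document"; such values also go into the study database.
- The NCS sentence: "For the lab results that do not meet the CTC for reporting as an AE, they will be considered not clinically significant (NCS").

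Section 10.3.2 (Laboratory Test Assessments) then adds: "Any abnormal laboratory test result considered clinically significant by the Investigator must be recorded".

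Section 12.2.1 makes safety the primary endpoint, in three parts: AE incidence, SAE incidence and "specific laboratory abnormalities (worst grade) in each treatment arm". It also defines TOX as a grade 3 or higher AE, at least possibly related, in the first 6 weeks of therapy. A steroid-treatable event counts only if it has not improved to grade 1 or better within 2 weeks. A separate success rule asks for at least 13 of 15 subjects without a grade 3 or higher AE that forces a delay of surgery. Section 5.3 states that the trial is open-label.

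**The concern.** The definition and the exclusion make AE status turn on clinical judgement when a value is asymptomatic and untreated. The grading sentence makes it turn on the CTC grade. The same value can therefore be an AE under one rule and go unrecorded under the other.

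This type of value is expected in the trial. Section 8.1 has provisions for grade 3 and grade 4 amylase or lipase abnormalities without symptoms, and Section 3.3.2 reports that the only grade 4 event in the cited HCC nivolumab trial was a raised lipase.

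AE incidence is a named component of the primary endpoint. Section 12.2.1 uses TOX for trial monitoring and for decisions about future trials, and Section 12.6 has toxicity reported after every 5 evaluable patients per arm. If recording differs between patients or arms because the assessor knows the treatment, both counts can shift, and the AE data alone would not show it.

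**Working it through.** The documents state no figure for this point, so the check sets the rules side by side.

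**Step 1. Apply each rule to an asymptomatic, untreated value that is new or has worsened since the first dose.**

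| Value | Definition | Exclusion | Grading sentence | NCS sentence | Section 10.3.2 |
|---|---|---|---|---|---|
| Meets CTC, judged significant | AE | does not apply | document | silent | record |
| Meets CTC, judged not significant | not an AE | do not document | document | silent | no requirement |
| Does not meet CTC | not an AE if classed NCS | do not document if the investigator agrees | does not apply | NCS | no requirement if NCS |

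The conflict lies in the second row. A value that is symptomatic or treated is an AE by definition. A value that was already present and has not worsened falls outside the grading sentence.

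**Step 2. Ask whether the NCS sentence settles the second row.** It says that results below CTC are not clinically significant. It does not say the converse, that every result meeting CTC is significant. It cancels neither the definition nor the exclusion, and Section 10.3.2 returns to investigator judgement. The conflict is not expressly resolved.

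**Step 3. Trace the second row to each safety measure.**

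- *AE incidence, all grades:* affected.
- *SAE incidence:* Section 10.3.1.5 requires any potential drug-induced liver injury that meets its transaminase and bilirubin definition to be reported as an SAE, so that pattern is caught separately.
- *TOX:* affected if the value is grade 3 or higher, at least possibly related, within the 6-week window and not removed by the steroid exception. TOX is defined on AEs and needs an attribution. Section 10.3.1.5 lists attribution among the items recorded for an AE, so a value never documented as an AE has none.
- *Worst-grade laboratory abnormalities:* listed separately from AEs. Section 12.2.1 neither names the abnormalities nor gives their data source. This part is affected only if it is compiled from AE records.
- *13-of-15 success rule:* requires an event serious enough to delay surgery. Such an event would hardly be judged not clinically significant, so the rule is largely insulated.

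**The case against.** The strongest reply is that the section can be read coherently. NCS means below CTC, the exclusion applies only to such results, and every new or worsened value that meets CTC is documented. The recommended recording grid in the same section supports this: it includes grade 3 to 5 events at every attribution level for Phase I and Phase II. This may well be the intention. But the reading has to be supplied, because the definition and the exclusion still stand as written, and the grid sorts events by grade and attribution without saying which laboratory values are AEs.

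A second reply is that laboratory results enter the safety assessment directly (Sections 10.2.2 and 12.5) and that worst-grade abnormalities are a separate endpoint component. This stands. It would be wrong to say that the laboratory tables must miss these values.

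A third is that TOX rests on investigator attribution in any case, has no numerical boundary, and that no between-arm safety test is planned. This also stands: a single recording rule would not remove judgement from TOX. It would make the judgement visible, because the event would be on record with its attribution.

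Three stronger readings are tempting, and the documents support none of them.

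- *About 3 patients per arm.* Section 3.3.2 reports grade 3 liver-enzyme elevations in 9 patients. With the 42 response-evaluable patients as an assumed denominator, 9/42 = 21.4%, and 0.214 × 14 = 3.0 or 0.214 × 13 = 2.8. With an assumed 60, 9/60 = 15%, and 0.15 × 13 = 2.0. But the safety denominator is not given, and the figure needs every elevation to be asymptomatic, untreated and judged insignificant, which Section 3.3.2 does not say. It also ignores the 6-week window and the steroid exception. Liver enzymes are a poor example, since Section 8.1 ties drug-related elevations to discontinuation thresholds; lipase is the fairer one.
- *The success rule is undermined.* With an assumed 10% failing for other reasons, P(at least 13 of 15) = 0.816. If a further independent 10% were counted or not according to the rule, the per-patient success probability would be 0.90 × 0.90 = 0.81 and P would be 0.436. Both rates are invented, and the calculation lets every such event count although the rule counts only those that delay surgery.
- *The decision to stop enrolment was biased.* Section 12.1 says that the principal investigator stopped enrolment because the safety endpoint had been reached. Nothing shows that this turned on undocumented laboratory values.

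**Conclusion.** The point holds in a limited form. Section 10.3.1.5 contains two incompatible rules for asymptomatic, untreated laboratory values that are new or worsened and meet CTC. AE incidence, and TOX where the value is grade 3 or higher and related, depend on which rule is followed, and one rule rests on the judgement of an unblinded principal investigator.

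The size cannot be estimated. The documents do not say how many such values are expected, how many would be judged not significant, or which reading was used in practice. If the grade-based reading was used throughout, the effect on the counts is nil. The conclusion assumes only that the definition, the exclusion and Section 10.3.2 mean what they say. This is a cheap improvement to a primary-endpoint component and does not put the 13-of-15 criterion in doubt.

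**What to change.** Keep one rule, and change all the places that carry the other; removing the exclusion alone would leave the conflict standing.

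1. Amend the definition and the exclusion in Section 10.3.1.5, and the recording sentence in Section 10.3.2, so that every new or worsened laboratory value of CTCAE grade 3 or higher is recorded as an AE. Record clinical significance and attribution as separate fields.
2. State the single rule that applies to grades 1-2, since AE incidence includes them.
3. In Section 12.2.1, name the specific laboratory abnormalities. Derive their worst grade, and the laboratory grades used for TOX, from the recorded values by CTCAE 4.0.

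The cost is small: the laboratory tests are already scheduled in Section 10.0, and the derivation can be applied before the final analysis. The downside is that reported grade 3+ rates may rise. Attribution remains a judgement, but a recorded one.
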